## Premise

### Proprioception

Proprioception represents the ability of the central nervous system to perceive the position and movement in the space of the body and its parts. It is very important both for a control mechanism on the correct execution of the movement, and for a mechanism of possible correction in the case in which, unexpected external phenomena, are to disturb the strategically programmed motor projects. The term proprioception has been used incorrectly as a synonym and interchangeable with kinesthetic, sense of common position, balance and reflexive articular stability. The term was coined by Sherrington in 1906 (70) from "receptus" (act of receiving) and "propius" (from himself) to define the sense of perception of body position understood as "conscious awareness", literally the "conscious" awareness, the awareness of the position of the limbs in space. Proprioception is defined as the sense of position and movement of the limbs and of the body that is independent of sight. It is an important component of the mechanisms that control and stabilize posture, ie the ability to maintain a position of the body and limbs and their orientation in space.

Continuous postural "adjustments" are required to perform a movement. These adjustments appear even more important in sporting activities, but the same applies when switching from a bipedal support to a monopodal support, or when climbing stairs. They immediately implement automatisms that "rearrange" the body in space.

It is not a matter of voluntary responses, which would take too long a time, but of unconscious automatisms: there is an already established "program" that the organism applies without effort. All this information reaches the central nervous system, where an answer is processed, which is immediately "postponed" to the muscles, where it translates into the execution of inexpensive and coordinated movements. We can distinguish two components of proprioception: a conscious called "proprioception" and an unconscious called "archaeoproprioception".

The conscious component provides the sensation of joint position (position in which a limb is located) and the sensation of joint movement. The information coming from conscious proprioception is transmitted through the backbone and partly through the spino-cervical tract, and is used to facilitate the most complex motor activities. The unconscious archaeoproprioception is the basis of the reflexes that make the body stable. It is an automatic system that does not involve consciousness. When you walk, you realize the surrounding environment without thinking of the muscles that move, balance, posture and everything works automatically. It affects the most primitive structures developed in the course of evolution: the spinal cord and the trunk of the brain, brain, cerebellum, medulla oblongata. The unconscious proprioception is important in the coordination of the simplest motor activities and in the maintenance of posture.

So proprioception is a complex anatomical structure, which consists of nerve centers and pathways and structures that respond to commands coming from the nervous system; there is a continuous exchange of messages between the external and internal environment, almost a telephone exchange that distributes information between muscles, tendons and the central nervous system.

The tibio-tarsic articulation has various functions: support of body load, movement, static and dynamic control, allows running, walking, jumping, landing from a jump absorbing the impact. And, no less important, it plays a fundamental role in providing a stable but flexible support base, through biomechanical compensation mechanisms, in the coordination of hip and knee movement.

Therefore, the tibio-tarsic is a joint of central importance for the implementation of the mechanisms of body proprioception.

## Proprioception and ankle

### Ankle instability

Ankle instability refers to a condition of weakness, more frequently arising after one or more distortional traumas. The patient reports it as a subjective feeling of insecurity and failure of the tibio-tarsal joint.

Ankle sprain is one of the most frequent traumas; in North America the prevalence is about 1 in 10,000 per day in the general population; in sports patients the percentage rises considerably, reaching about 40% of total sports injuries. The reason is related to the forces applied during competitive activity and body weight.

The most frequent distortion trauma is that in inversion, which occurs during a plantar flexion movement and inversion of the foot with an excess of supination of the ankle and extrarotation of the tibia.

This traumatic movement leads to a stretching or injury of the lateral ligament compartment, consisting of the anterior peroneo-astragalic ligament, peroneo-calcaneal and posterior peroneal-astragalic ligaments.

Approximately 40% of patients who have undergone an ankle sprain will experience relapsing sprains due to instability generated by the first trauma. This group of patients is most at risk of developing an early osteoarthritis due to the excessive consumption of articular cartilage.

Intrinsic predictive factors of ankle sprain include anatomical features, functional deficits in isometric strength, flexibility, joint proprioception, muscle reaction time, postural stability, dominant limb, Body Mass Index (BMI) and previous distortive trauma.

Despite the extensive research developed in recent years, to date a common vision for the assessment of ankle instability has not yet been reached. This is due to the multitude of tools and techniques used to quantify postural stability.

In general, the methods used today test the static, dynamic and functional postural stability. Clinical tests (mCTSIB, BESS) and instrumental tests (test with platform) are used to quantify the static stability; to quantify the dynamic stability a change of position of the patient is generated (change of direction or a jump) or a perturbation of the support surface is created. To quantify the functional stability we use exercises using a support base able to create continuous position changes (gait analysis).

## 2. OBJECTIVES

The aim is to study the effectiveness of the ankle external ligament reconstruction according to the modified Bröstrom-Gould technique through the study of the postural control with:

- a computerized oscillating platform, Delos device ([www.delos-international.com](http://www.delos-international.com)), in particular in its proprioceptive component;
- using the Modified clinical test Star Excursion Balance Test (mSEBT);
- through evaluation questionnaires (FAAM, AOFAs, SPPB).

To date, in fact, there are scientific works, also produced by our Institute (Giannini et al., 2014), which evaluated patients pre- and post-operatively, but only through clinical score.

Patients will then undergo a preoperative evaluation and a second evaluation at an average time of 4 months from the surgery.

Primary outcome: evaluation of the modified Bröstrom-Goulde technique for ankle external ligament reconstruction.

Secondary outcome: comparison between Delos and mSEBT as stability and proprioception evaluation techniques.

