### mSEBT (modified Star Excursional Balance Tests)

In recent years within the orthopedic and physiatric discipline the interest in the development of tests that allowed to evaluate the stability of the ankle joint can be used, which can be used to quantify the ligament damage resulting from a trauma or that allow to evaluate the improvement after a surgery or rehabilitative treatment.

The Star Excursional Balance Test (SEBT) is a clinical test designed to assess the dynamic physical performance of ankle. The first literary references date back to 1998 and the test provided, remaining in balance with the ankle in the studio, reaching the maximum possible distance with the contralateral foot along the well-determined axes (see figure below) by making 12 attempts in each direction in two distinct days.

More recently, through statistical analysis studies, a large data redundancy has been demonstrated with too great a difference in the various attempts along the 8 directions. Therefore, the latest studies suggest to perform the test along only three axes (anterior, posteromedial and posterolateral). The three axes will be arranged through an angle of 135 ° (between the anterior line and the posteromedial line, between the anterior and posterolateral line) and an angle of 90 ° (between the posteromedial and the posterolateral). Moreover, the attempts to be carried out have been reduced to 3 for each direction that can be performed after a few minutes of rest making the test run easier with a timing of less than 60 minutes. This is referred to as the modified Star Excursional Balance Test (mSEBT). You will then get 3 final values, one for each direction that will be the result of the average of the three tests performed. The results obtained will then be standardized for the length of the patient's limb, so as to obtain comparable values between the different patients. The length of the limb will be calculated at the supine patient, from the antero-superior iliac spine (SIAS) to the apex of the medial tibial malleolus; the length will be calculated on both limbs twice and an average of the obtained values will be made.

To standardize the mSEBT, the average value of each single direction will be divided by the average length of the limb and multiplied by 100%.

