To evaluate an effective improvement of joint stability, the outcome of the post-operative test must have a percentage increase. The percentage proposed by Remko van Lieshout et al. in his study he is at least 6.9% for the right limb and 5% for the left (in a patient with a right-hand limb). While Fitzgerald A. et al. they considered valid percentages between 2.95% and 9.4% and Filipa et al. 1.75% and 9.5% to attest to an improvement in post rehabilitative joint stability. Therefore, in our work, in the light of the indicated values, we will adopt those proposed by Remko van Lieshout et al. being also the most recent study on the subject.

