The SF12 test is the short version of the SF-36 (link) questionnaire. Through 12 of the 36 questions of the original questionnaire it allows to investigate the two synthetic indexes, PCS Physical Component Summary for the Physical State and MCS Mental Component Summary for the State of Mental. The strong points of this questionnaire are the brevity and the relative ease of use. In Italy, the questionnaire was used inter alia in 2000 in a ISTAT multiscopo survey on the health status of Italians and a reference database is available with data on a sample of 61.434 representative subjects of the Italian population. Also for this short form the literature is rich in experiences and studies that prove its validity and reliability.

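### The primary outcome names the operation rather than a variable, every outcome is tested at 0.05 without ordering, and the adopted mSEBT threshold is not carried into the analysis

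*Combined protocol and SAP*

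**What the plan says.** All references are to the combined protocol and SAP.

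- **Section 2, Objectives.** The primary outcome is given as "Primary outcome: evaluation of the modified Bröstrom-Goulde technique for ankle external ligament reconstruction". The aim is framed as a study of postural control with Delos, "in particular in its proprioceptive component", with the mSEBT, and "through evaluation questionnaires (FAAM, AOFAs, SPPB"). It adds that earlier work assessed patients by clinical score alone. The only other designated outcome is "Secondary outcome: comparison between Delos and mSEBT as stability and proprioception evaluation techniques".
- **mSEBT section.** On scoring: "You will then get 3 final values, one for each direction". Each value is divided by limb length; no composite is defined. On interpretation: "To evaluate an effective improvement of joint stability, the outcome of the post-operative test must have a percentage increase". The values adopted from a cited reproducibility study are "at least 6.9% for the right limb and 5% for the left (in a patient with a right-hand limb").
- **Clinical score.** SF12 is described as yielding "the two synthetic indexes, PCS Physical Component Summary for the Physical State and MCS Mental Component Summary".
- **Visits and examinations scheduled by the study.** Delos is used for both static and dynamic evaluation before and after surgery. SF12 is collected at both visits, although the aim in section 2 does not list it.
- **Study sample (the statistical text).** A repeated-measures ANOVA is planned for continuous variables in general. A percent Delta score is computed for every continuous outcome and related to categorical variables and, by Spearman correlation, to continuous or rank variables. One significance level, 0.05, applies to all tests. No primary variable, hierarchy, multiplicity rule or responder definition appears.

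**The concern.** A primary outcome has to identify the measurement on which the conclusion rests. Here it identifies the treatment under study. If AOFAS improved and Delos did not, or the reverse, nothing in the available text would say whether the technique had been shown to be effective. With every test judged at 0.05, a significant result on any one instrument could be put forward as the main finding, and the chance of obtaining at least one by luck is above 5%.

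The mSEBT threshold raises a related problem. It is the plan's one stated standard for effective improvement, yet no planned analysis counts the patients who reach it. The text also leaves open which of the three direction values must reach it, and how it applies to patients other than the one described (read here as right-dominant).

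**Working it through.** **Reproducing the plan's figure.** The plan states no familywise error rate, so there is nothing to reproduce. Its only relevant number is 0.05 per test.

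**Counting the outcomes.** The split is this review's own, from the listed sections.

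- Instruments in the aim (section 2): Delos, mSEBT, FAAM, AOFAS, SPPB = 5.
- The same five, with Delos split into static and dynamic (visit schedule) and mSEBT into three directions (mSEBT section): 2 + 3 + 1 + 1 + 1 = 8.
- Adding the two SF12 summary scores (Clinical score), a sixth instrument outside the aim: 8 + 2 = 10.

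**Chance of at least one significant result if no outcome truly changes.** Assumptions: one test per outcome, normal test statistics, and a common correlation ρ. The documents give no correlations, so a range is shown.

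Independent outcomes: 1 − 0.95^k.

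- k = 5: 1 − 0.774 = 0.226
- k = 8: 1 − 0.663 = 0.337
- k = 10: 1 − 0.599 = 0.401

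Correlated outcomes, with c = 1.960 and u a standard normal variable with density φ:

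1 − ∫ [Φ((c − √ρ·u)/√(1−ρ)) − Φ((−c − √ρ·u)/√(1−ρ))]^k φ(u) du

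For favourable results only (nominal 2.5% per test), the second Φ term is dropped. With ρ = 0 this becomes 1 − 0.975^k.

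| Outcomes | Direction | ρ = 0 | 0.3 | 0.5 | 0.7 | 0.9 |
|---|---|---|---|---|---|---|
| 5 | either | 0.226 | 0.209 | 0.183 | 0.148 | 0.102 |
| 8 | either | 0.337 | 0.300 | 0.250 | 0.191 | 0.119 |
| 10 | either | 0.401 | 0.351 | 0.287 | 0.213 | 0.128 |
| 5 | favourable | 0.119 | 0.105 | 0.091 | 0.074 | 0.051 |
| 8 | favourable | 0.183 | 0.152 | 0.125 | 0.095 | 0.060 |
| 10 | favourable | 0.224 | 0.178 | 0.144 | 0.107 | 0.064 |

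Even at ρ = 0.9 the chance is at least double the nominal rate: 0.102/0.05 = 2.0 in either direction, and 0.051/0.025 = 2.0 for favourable results.

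**Following the threshold through the plan.** The mSEBT section requires a percentage increase and adopts 6.9% (right) and 5% (left). The statistical text computes (T1 − T0) × 100/T0, a scale to which such a threshold could be applied. It then uses that score only to study the effect of other variables. The chi-squared/Fisher comparison is described as pre- versus post-operative, which does not suit a responder status that exists only after surgery. So no listed analysis uses the threshold.

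**The case against.** The strongest reply is that section 2 is not neutral. It speaks of postural control, singles out the proprioceptive component of Delos and contrasts the study with work based only on clinical scores. This points to the instrumented tests as the intended contribution and makes it less plausible that a questionnaire would be presented as primary. That stands as emphasis, but it designates nothing: the phrase qualifies Delos within an unranked list, no Delos index is named anywhere in the available text, and Delos itself is evaluated both statically and dynamically.

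A second reply is that the error rates assume no outcome changes after reconstruction and rehabilitation. This also stands. If some outcomes truly change, the error concerns only the others. The figures are illustrations, and a reader might wrongly take 40% as this trial's error rate. It requires ten independent outcomes, including SF12, which lies outside the aim; the five instruments in the aim give eight by the count used here.

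A reader might also infer that the mSEBT threshold plays no part in the conclusion. The text does not support that. The mSEBT section gives it an interpretive role; what is missing is an analysis that carries it out, and the details needed to do so.

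Finally, it is tempting to read the ANOVA's two groups as pre- and post-operative. That wording is attached to the Mann-Whitney and chi-squared tests. What the ANOVA groups are is a separate question and is not settled here.

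**Conclusion.** The point holds and should be corrected before analysis. In the available text no variable is designated primary, no instrument is ranked, and all tests share the 0.05 level without adjustment. The stated secondary outcome compares two measurement methods and does not order the efficacy measures.

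The size depends on the count and on assumed correlations from 0.9 to 0. It is 10–23%, 12–34% and 13–40% for five, eight and ten outcomes, or 5–12%, 6–18% and 6–22% for favourable results against a nominal 2.5%. These rest on no true change and one test per outcome. The gap in the decision rule does not depend on them: whatever the error rate, the plan cannot say which result answers its main question.

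On the threshold, the supportable conclusion is narrower: it is adopted for interpretation but not carried into the statistical text, and its application by direction and by limb dominance is unspecified.

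**What to change.** **Primary variable (section 2 and Study sample).** Before analysis, name one: a single Delos proprioceptive index, which is closest to the emphasis in section 2. If none can be fixed in advance, use the operated-limb mean of the three limb-length-normalised mSEBT directions, defined as a new composite. Test its T0 to T1 change with a paired test at two-sided 0.05, give a 95% CI, and rest the effectiveness conclusion on it. A paired test fits because one treated cohort is measured twice.

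**Other efficacy outcomes.** Label them secondary, either exploratory with estimates and CIs, or Holm-adjusted. Either choice cures the defect. Keep Delos versus mSEBT as a separate methodological objective.

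**Threshold (mSEBT section and Study sample).** As a supporting analysis, report the proportion of patients whose mSEBT percent Delta meets the adopted threshold for the operated limb, with an exact 95% CI. State beforehand which direction or composite it applies to and how patients who are not right-dominant are handled.

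**Cost.** Wording changes in three places (section 2, the mSEBT section, Study sample), and recording of operated side and limb dominance at the scheduled visits. The primary test keeps the full 0.05. Holm adjustment would cost power on secondary outcomes. If Delos gives exactly one static and one dynamic measure, and single mSEBT directions are descriptive, seven tests remain. With a Delos index primary they are the other Delos measure, the mSEBT mean, FAAM, AOFAS, SPPB, PCS and MCS; with the mSEBT mean primary, the two Delos measures replace the first two. The first step is 0.05/7 = 0.0071 (z = 2.690), so an effect with 80% power at 0.05 has Φ(1.960 + 0.842 − 2.690) = Φ(0.112), about 54%, at that step.

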### 3. STUDY DESIGN

Will be included in the study all the patients who undergo surgery for lateral capsular-ligament instability during 18 months after EC approval (probably end on August 2019), in accordance with the criteria specified below. Each patient will sign an informed consent for participation in the study.

Inclusion and exclusion criteria for patients enrolled in the study

The study population consists in patients with chronic post-traumatic lateral ankle instability who must undergo ankle external ligament reconstruction.

#### **Inclusion criteria:**

Patients will be recruited according to the following inclusion criteria:

- patients who must undergo surgery;
- patients of both sexes aged between 18-40 years;
- patients who have given their informed written consent to participate in the study;
- patients who have given their readiness to reach the Institute to perform the 4-month check-up.

#### **Exclusion criteria:**

- patients with  $BMI > 30 \text{ kg} / \text{m}^2$ ;
- patients with rheumatoid arthritis;
- patients with chronic inflammatory joint diseases;
- patients with pre-existing abnormalities of the ambulatory kinematics (amputations, neuro-muscular diseases, polio, hip dysplasias);
- patients with Severe arthrosis of the ankle (Kellgren-Lawrence  $> 3$ );
- patients with Severe knee arthrosis (Kellgren-Lawrence  $> 3$ );
- patients with ACL injury;
- patients with severe postural instability;
- patients with cognitive impairments;
- patients with concomitant neurological diseases.

### 4. MATERIALS AND METHODS

The study of posture and control of movement in humans requires technological supports capable of providing accurate, reproducible and repeatable information on displacement and / or position in real time.

The Delos Postural Proprioceptive System is an oscillating platform that uses electronic tilting tables (on a single axis or three axes) at high frequency which allows very short stopping and reversal times. Furthermore it is possible to assign position tasks and maintain a specific inclination.

Moreover, the combination of tilting and translating table with an electronic sensor that provides visual feedback in real time, greatly increases the number of biomechanical situations to be managed in the unit of time. The inclination of the table, which at every moment is communicated through the track on the monitor, hooks the subject to a new situation to be managed. The nerve centers, thanks to the high flow of afferent signals, are trained to interpret them correctly and to provide adequate responses faster and faster. The visual feedback involves a flow of high frequency proprioceptive signals able to reprogram the postural control and movement system, considerably higher than a situation managed with eyes closed or with the aid of a mirror. In fact, with closed eyes there is a greater commitment on the part of the other sensory analyzers, but in the absence of visual feedback the number of biomechanical situations to be managed is drastically reduced with consequent reduction of the flow of proprioceptive signals, while the use of a mirror as Visual feedback is of no use as it is a complex piece of information that requires long time for cortical processing to be used. For this reasons this system can be used for diagnose and quantify ankle instability.

### mSEBT (modified Star Excursional Balance Tests)

In recent years within the orthopedic and physiatric discipline the interest in the development of tests that allowed to evaluate the stability of the ankle joint can be used, which can be used to quantify the ligament damage resulting from a trauma or that allow to evaluate the improvement after a surgery or rehabilitative treatment.

The Star Excursional Balance Test (SEBT) is a clinical test designed to assess the dynamic physical performance of ankle. The first literary references date back to 1998 and the test provided, remaining in balance with the ankle in the studio, reaching the maximum possible distance with the contralateral foot along the well-determined axes (see figure below) by making 12 attempts in each direction in two distinct days.

More recently, through statistical analysis studies, a large data redundancy has been demonstrated with too great a difference in the various attempts along the 8 directions. Therefore, the latest studies suggest to perform the test along only three axes (anterior, posteromedial and posterolateral). The three axes will be arranged through an angle of 135 ° (between the anterior line and the posteromedial line, between the anterior and posterolateral line) and an angle of 90 ° (between the posteromedial and the posterolateral). Moreover, the attempts to be carried out have been reduced to 3 for each direction that can be performed after a few minutes of rest making the test run easier with a timing of less than 60 minutes. This is referred to as the modified Star Excursional Balance Test (mSEBT). You will then get 3 final values, one for each direction that will be the result of the average of the three tests performed. The results obtained will then be standardized for the length of the patient's limb, so as to obtain comparable values between the different patients. The length of the limb will be calculated at the supine patient, from the antero-superior iliac spine (SIAS) to the apex of the medial tibial malleolus; the length will be calculated on both limbs twice and an average of the obtained values will be made.

To standardize the mSEBT, the average value of each single direction will be divided by the average length of the limb and multiplied by 100%.

To evaluate an effective improvement of joint stability, the outcome of the post-operative test must have a percentage increase. The percentage proposed by Remko van Lieshout et al. in his study he is at least 6.9% for the right limb and 5% for the left (in a patient with a right-hand limb). While Fitzgerald A. et al. they considered valid percentages between 2.95% and 9.4% and Filipa et al. 1.75% and 9.5% to attest to an improvement in post rehabilitative joint stability. Therefore, in our work, in the light of the indicated values, we will adopt those proposed by Remko van Lieshout et al. being also the most recent study on the subject.

